The High Intensity exercise to Promote Accelerated improvements in Cardior Espiratory fitness (HI-PACE) study will evaluate the effect of exercise intensity on CRF and insulin sensitivity in obese (BMI: 30-45) African Americans (40-65 yrs.) with at least 1 additional T2D risk factor. Participants (n=60) will be recruited in collaboration with the ECU Center for Health Disparities, and subsequently randomized to moderate intensity (MOD-INT, n=20) or high intensity (HIGH-INT, n=20) aerobic exercise training, or to a control group (CON, n=20) for 24 weeks. Supervised exercise training will be performed at a heart rate associated with ~50% and ~75% of VO₂ max in the MOD-INT and the HIGH-INT groups, respectively at the same exercise volume of 600 MET-minutes per week (consistent with public health recommendations). The primary outcome is the change in CRF, which will be assessed at baseline, mid-intervention, and follow-up. Insulin sensitivity will be measured via an intravenous glucose tolerance test at baseline and follow-up. Other secondary measures include mitochondrial oxidative capacity using infrared and measurements on muscle biopsies (PGC-1 α and other indices of mitochondrial content), the expression of a protein involved with insulin action (GLUT-4 expression) in skeletal muscle as well as systemic inflammation, adiposity, quality of life and exercise enjoyment measures.

Specific Aims: We seek to provide evidence in obese African American that:

- High intensity aerobic training will lead to greater increase in CRF compared with moderate intensity
 aerobic exercise
- High intensity aerobic exercise training will lead to greater improvements in insulin sensitivity compared with moderate intensity aerobic exercise

In accordance with the intent of this mechanism, the HI-PACE study will provide clinically relevant (CRF/insulin sensitivity) and mechanistic data (skeletal muscle), allow us to power outcome variables, and provide recruitment, retention and exercise adherence rates in African Americans for a future R01 proposal.

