(indirect calorimetry) to adjust the rate predicted from ACSM equations. This has never been performed in an exercise intensity study, and will allows us to more accurately match exercise volume in both groups Skeletal muscle measures will be evaluated to support conclusions on whole body CRF and insulin action **HI-PACE** will be the first study to compare the health benefits of moderate and high intensity exercise training on T2D risk factors specifically in African Americans. The present research will have high public health implications given the substantially greater T2D risk in African Americans compared to Caucasians, and the under-representation of African Americans in physical activity research. The results of HI-PACE will allow us to adequately power our main primary and secondary outcomes to inform the design of an R01 application on exercise intensity in African American adults with a larger array of secondary outcomes. Completion of HI-PACE and the subsequent R01 will likely impact future physical activity recommendations, and will help guide health professionals on the type of exercise to recommend to obese African Americans with high T2D risk. **3.** Approach: The HI-PACE study will enroll 60 sedentary obese African Americans (BMI: 30-45 kg/m², age 40-65 vrs). We will randomize participants to moderate intensity (MOD-INT, n=20), high intensity (HIGH-INT, n=20), or a control group (CON, n=20) for 24 weeks. The primary outcome measure will be the change in CRF following the intervention. Main secondary outcomes include insulin sensitivity measured via an intravenous glucose tolerance test (IVGTT), mitochondrial capacity, skeletal muscle measurements, body fat, c-reactive protein, and psychological outcomes (quality of life/exercise enjoyment).

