
physical activity, and charge status of all active devices in the study. We will utilize food frequency questionnaires (FFQ) ⁶² to measure estimated daily intake (kilocalories, macronutrients, and micronutrients). 7. Statistical Considerations: Initial CRF will be compared for the three groups using side-by-side boxplots. Side-by-side boxplots will also be made for males and separately for females as we expect the max O2 to be greater for males. Numerical summaries for the boxplots along with mean and standard deviation will be recorded. Outliers and other observations requiring additional scrutiny will be identified. These steps will be repeated for the measurements taken post intervention and for the differences. The groups will be compared in terms age and other covariates using graphs (boxplots for numeric variables and segmented bar plots for categorical data) and numeric summaries. Assuming the descriptive analyses reveal no serious violations of the assumptions, ANOVA will be used to analyze the differences in CRF. In addition to using contrasts for group comparisons, confidence intervals for the difference in means will be reported. Both one-way (factor Group) and two-way (Group and Sex) ANOVA will be used. The analyses described for CRF would also be applied to insulin sensitivity, and other secondary outcomes. Data will be analyzed on an intention to treat basis. We expect attrition rate to be approximately 10-15%. Using -.112, .124, and .200 L/min as the means for the three groups based on previous data ³⁵, a common standard deviation of .250 L/min, and significance level .05, the power ranges from .85 for 15 participants per group to .96 for 20 participants per group. 8. Experience of PI: The PI has 33 publications on exercise training and T2D/CVD risk factors, and is a former NIDDK T-32 postdoctoral fellow (Pennington Biomedical, Mentor: [name].). He has worked on a completed trial on exercise intensity and visceral fat ⁶³. His publications include 3 papers on exercise intensity ^{35,64,65}, 5 papers on racial health disparities ^{9,21,66-68}, and 4 papers dealing with cardiorespiratory fitness as a risk factor for disease ^{21,65,69} (3 specifically on CRF in adults with T2D ⁷⁰⁻⁷²), and a recently published review paper on racial disparities in T2D²⁶. He has been awarded an NIH loan repayment award from NIMHD, and was recently accepted to the NHLBI sponsored PRIDE summer research program for health disparities research. 9. Potential Pitfalls: Recruitment of the necessary sample of African Americans is a potential concern. However, the CHD has documented success with recruitment of African Americans. The PI and the CHD will closely monitor recruitment trends. If the recruitment of participants is below the expected rate, we will develop new recruitment plan to meet the necessary study sample. As the PI is a second year faculty member, another potential pitfall is that the study team has not worked extensively together on a clinical trial. As noted in the study flow diagram (below), during start-up, extensive study planning will take place inclusive of a manual of procedures (MOP), standard operating procedures (SOP), and simulations of data collection of all study visits/databases prior to the start of recruitment. Additionally, Drs. [name] and [name] are co-investigators on the PI's ongoing AHA funded exercise trial at ECU, which currently has 92% exercise adherence (6 month exercise intervention), which suggests the PI is capable of implementing an exercise intervention at his new institution. While the PI will assume complete responsibility of leading this trial, [name] (expertise: large exercise trials/insulin sensitivity, muscle biopsies) will serve as faculty mentor, and the research team will engage in regular study meetings to closely monitor the progress of important indicators of study success (e.g. recruitment rates, adherence to exercise levels and intensity, etc.). If the results of HI-PACE are not supportive of what we have hypothesized on CRF, the secondary measures (insulin sensitivity, skeletal muscle measures, body composition) and archived blood/muscle samples are potential sources to support an R01 application. 10. Conclusion: The HI-PACE study has high public health relevance due to the increased disease burden of T2D and the lack of exercise training studies in African Americans. HI-PACE will be the first study to compare two exercise training programs on T2D risk factors in obese African Americans, and has the potential to influence future physical activity recommendations. We will also obtain valuable psychological parameters of quality of life and enjoyment of exercise, which will help determine whether high intensity aerobic exercise is a feasible strategy over a six month period to improve health outcomes in African Americans. In accordance with the goals of this funding mechanism, the specific direction of the R01 will be dependent on the results of the

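### Intention to treat is claimed with about 10-15% attrition expected, but the stated ANOVA on CRF change can use only people with a post-intervention test, and week-12 CRF has no role in that analysis

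*Combined protocol and SAP*

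**What the plan says.** Section 7 (Statistical Considerations) sets the principle and the expected loss together: "Data will be analyzed on an intention to treat basis. We expect attrition rate to be approximately 10-15" per cent. The method is "ANOVA will be used to analyze the differences in CRF", and "Both one-way (factor Group) and two-way (Group and Sex) ANOVA will be used". The section names initial CRF, post-intervention CRF and the differences, and carries the method over: "The analyses described for CRF would also be applied to insulin sensitivity, and other secondary outcomes".

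On the outcome and its timing:
- Specific Aims: "The primary outcome is the change in CRF, which will be assessed at baseline, mid-intervention, and follow-up".
- Section 3 (Approach): "The primary outcome measure will be the change in CRF following the intervention".
- Assessment visits: CRF is scheduled at baseline, week 12 and week 24, and randomisation is stratified by sex.
- Exercise intervention: the week-12 test serves to update the training heart rate ranges. This is its only explicit use.
- IVGTT: insulin sensitivity is measured at baseline and follow-up only.

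The documents do not define the intention-to-treat set. They give no imputation rule, repeated-measures model, missing-data assumption or sensitivity analysis, and do not say whether people who stop training are tested at week 24.

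**The concern.** A baseline-to-post difference cannot be formed without the post value. With no rule for missing values, the ANOVA as described is an analysis of people who have a week-24 test, so the plan gives no means of meeting its intention-to-treat claim for the others.

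The first aim is the HIGH-INT versus MOD-INT comparison of CRF change. If people who respond poorly are more likely to leave, and this differs between the two exercise arms, the contrast among those tested is biased. The week-12 test, already scheduled, carries information about the missing week-24 values of anyone who leaves after it, and the stated method does not use it.

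The estimate will be carried forward. Section 2 says: "The results of HI-PACE will allow us to adequately power our main primary and secondary outcomes to inform the design of an R01 application".

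**Working it through.** **Inputs from Section 7.** 20 per arm; attrition about 10-15%; SD .250 L/min; significance level .05; and "Using -.112, .124, and .200 L/min as the means for the three groups based on previous data". The means are not labelled. Where an arm matters I assume the order CON, MOD-INT, HIGH-INT, so HIGH minus MOD is .200 − .124 = .076 L/min.

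**1. The plan's power figure.** Omnibus F power uses the noncentral F with λ = n·Σ(mᵢ − m̄)²/SD² and df 2 and 3n − 3. Here m̄ = .0707 and Σ(mᵢ − m̄)² = .0529.
- n = 20: λ = 20 × .0529/.0625 = 16.9; power .957. This agrees with the stated .96.
- n = 15: λ = 12.7; power .878. The plan states .85, which is lower. I did not reproduce that end, but nothing below depends on it.

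**2. Expected loss.** 60 × .10 = 6 and 60 × .15 = 9. If losses are even and every leaver misses week 24 (both assumptions), 20 × .85 to 20 × .90 = 17 to 18 per arm remain. Power is .919 at 17 and .934 at 18. The 6 to 9 is not a ceiling: at a true rate of 15%, the binomial chance of losing more than 9 of 60 is .41.

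**3. Precision of HIGH minus MOD.** SE = .25·√(2/n): .0857 at 17, .0833 at 18. With df 3n − 3, the 95% CI half-width is .172 and .167 L/min.

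**4. Illustrative bias of the ANOVA contrast.** None of these assumptions is in the documents. In one exercise arm, logit P(leave) = a − ln(2)·z, where z is week-12 change in SD units (odds ratio 2 per SD). In the other arm dropout is random. The correlation ρ between week-12 and week-24 change is .5 to .7. Bias = ρ × .25 × E[z | stays], by numerical integration.

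| Dropout in affected arm | ρ = .5 | ρ = .7 |
|---|---|---|
| 10% | .0083 | .0116 |
| 15% | .0122 | .0171 |

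The sign is positive if HIGH-INT is affected and negative if MOD-INT is. In standard errors the range runs from .0083/.0833 = 0.10 to .0171/.0857 = 0.20. Against .076 it is 11% (.0083/.076) to 22.5% (.0171/.076). With the same mechanism in both arms the bias is zero at equal rates, and .004 to .006 in size at 15% versus 10%.

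**5. What week 12 recovers.** Monte Carlo, 20,000 runs per setting, 20 per arm, Monte Carlo error about .0006. If all leavers go after week 12, the mixed-model bias is within .002 of zero. If half go before week 12, about half the bias remains: .004 to .008, against .009 to .017 for the ANOVA. Under random dropout (proportion p) the SE ratio is √(1 − ρ²p): .987 (p = .10, ρ = .5) to .963 (p = .15, ρ = .7), a gain of about 1 to 4%.

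**6. Insulin sensitivity.** With two visits, every leaver contributes baseline only. With about 14% leaving and dropout depending on change (odds ratio 2 per SD), a two-visit model and ANOVA give the same bias when change is uncorrelated with baseline (.095 SD each), and nearly the same at correlation −.3 (.086 against .094).

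**The case against.** The plan nowhere says that people without a week-24 test are dropped. A reader might infer that it does, or that it contradicts its own intention-to-treat claim. The text supports less: the stated method cannot include them, and no other method is given.

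The power range goes down to 15 per arm, a 25% loss from 20, so attrition was allowed for in sample size. That stands, and lost power is not the complaint. The run-in week, make-up sessions and case managers should reduce loss, but they do not say how remaining losses are analysed.

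The illustrated bias is small against a CI half-width more than twice .076, and the documents contain no evidence of differential dropout. Both points stand. So does the point that the illustration favours the mixed model: dropout is made to depend on week-12 change, which the model conditions on, so near-zero bias for late leavers is built in.

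CRF at mid-intervention also appears in the paragraph on secondary outcomes, and Section 7 extends the CRF analyses to those outcomes, so a separate ANOVA of week-12 change is a possible reading. It would not help with missing week-24 values.

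Finally, this is a pilot of 60, and an elaborate missing-data programme would be out of proportion. That is fair, and the fix is kept short.

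**Conclusion.** The point holds as a cheap improvement that should be made. The intention-to-treat statement has no stated method behind it for roughly 6 to 9 of 60 people, and a measurement that could help is already scheduled.

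The size is modest: .008 to .017 L/min, or 0.1 to 0.2 standard errors, if response-dependent dropout affects one exercise arm under the assumptions shown. It is zero if dropout is random, or if mechanism and rate are the same in both arms.

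A reader might go further and infer that the trial will favour HIGH-INT, that it loses meaningful power, or that week 12 should become an endpoint. The documents support none of these. They give neither size nor direction of any bias, omnibus power stays at .919 or above at the expected attrition, and the primary outcome is change following the intervention.

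**What to change.** **Primary CRF analysis.** Use a repeated-measures mixed model on all randomised participants (baseline, week 12, week 24) with group, visit, group-by-visit, sex and sex-by-visit. The sex-by-visit term is what adjusts change for sex; it mirrors the planned Group-and-Sex ANOVA and the stratified randomisation. Report the week-24 HIGH-INT minus MOD-INT difference in change with its 95% CI.

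**Sensitivity analyses.** Keep the planned difference-score ANOVA. Add one simple missing-not-at-random analysis, for example multiple imputation giving leavers in all arms the control-arm mean change with residual variance retained.

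**Follow-up and reporting.** State that the scheduled week-24 assessment is sought from every randomised participant willing to attend, whether or not still training. Report missing week-24 values by arm, split into before and after week 12.

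**Insulin sensitivity.** A two-visit mixed model offers little protection. Rely on week-24 follow-up and the missing-not-at-random analysis.

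**Cost and limits.** A few sentences of analysis wording, standard software, a little more analysis work, and effort to bring back those who stop training. The model assumes missingness depends on observed data, and leavers before week 12 contribute only baseline.

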local community settings frequented by them; distribute these to their partners; advertise the project on the Center's African-American community website, Minority Health Matters; and maintain a phone number to answer potential-participants' questions. We will also utilize standard techniques (advertisement, ECU email server, flyering). 5. Pre-screening: After phone-screen, individuals will be invited to an orientation session, where we will provide information about the study design, procedures, and risks/benefits. Individuals interested in participation will be consented, and scheduled for run-in visits. Run-in visits: The purpose of the run-in visit is to ensure participants are able to make the time commitment to come to ECU approximately three times per week. In our past training studies, this run-in period has helped to obtain excellent training adherence by allowing potential participants to fully evaluate their ability to commit to study time demands. To simulate participation in HI-PACE, run-ins sessions will be scheduled 3 sessions per week over the course of one week, and duration will be similar to training sessions (~30-60 minutes). Study staff will verify sedentary status, and screen for other inclusion/exclusion criteria (e.g. medical history questionnaire/study surveys, BMI, waist circumference, blood pressure assessment, etc.). As a safeguard against low exercise adherence, participants will complete an exercise calendar (identification of expected exercise days/times, and potential back-up times). Participants will also complete a questionnaire on time commitments, child/elder care, distance from the exercise facility, motivations for exercise, family support.

Phone Screening : Age (40-65 yrs.), BMI (30-45), Diabetes (NO), Heart disease (NO), sedentary, African American (YES), Contact info

Orientation

-Informational session about study requirements -Obtain consent for screening and run-in visits

Run-in visits

-3 run sessions over 1 weeks to test participants ability to come to ECU 3 times per week - Verify inclusion criteria (ie: baseline physical activity, waist circumference, blood pressure). -Collection of FFQ and QOL questionnaires

SV1

- Obtain consent for main study - Physical exam/review of medications -Lipids, CBC, Chem panel, insulin

Baseline

- Weight, blood pressure, anthropometry, CRP, DEXA, Exercise test, mitochondrial measurements, muscle biopsy, IVGTT, FFQ, QOL -Randomization (CON, LOW-INT, HIGH-INT)

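### The stated power of .85 to .96 fits a three-group omnibus test driven by the control arm; for Aim 1, HIGH-INT versus MOD-INT, the same inputs give about 13 to 16%.

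*Combined protocol and SAP*

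**What the plan says.** The Specific Aims section makes CRF the primary endpoint ("The primary outcome is the change in CRF") and states Aim 1 as a comparison of the two exercise arms: "High intensity aerobic training will lead to greater increase in CRF compared with moderate intensity". Sixty participants are to be randomized equally to MOD-INT, HIGH-INT and control, 20 each.

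Section 7 (Statistical Considerations) plans one-way ANOVA by group and two-way ANOVA by group and sex on the CRF differences, with contrasts and confidence intervals for group comparisons. It expects 10 to 15% attrition. Its only power statement starts "Using -.112, .124, and .200 L/min as the means for the three groups based on previous data", adds "a common standard deviation of .250 L/min" and "significance level .05", and concludes that "the power ranges from .85 for 15 participants per group to .96 for 20 participants per group".

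The section does not say which test this power refers to, which mean belongs to which arm, or whether tests are one- or two-sided. No power is given for HIGH-INT versus MOD-INT, and no contrast is named as primary.

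**The concern.** A power figure computed from three means describes the chance of detecting some difference among three groups. Here the control mean lies far below the two exercise means, and these lie close together. Such a test can be well powered because exercise beats no exercise, whatever the effect of intensity. Aim 1 is about intensity.

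As the only power statement, in a plan whose first aim is HIGH-INT against MOD-INT, the .85 to .96 will be taken to cover that aim. Two opposite misreadings follow. A significant omnibus F could be taken as support for Aim 1. A non-significant HIGH-INT versus MOD-INT contrast could be taken as showing that intensity does not matter, on the belief that the trial was powered to see a difference.

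**Working it through.** **Inputs (Section 7 unless noted).** Means -.112, .124 and .200 L/min; SD .250; alpha .05; n = 15 to 20 per group. With 10 to 15% attrition from 20, 17 to 18 per group remain. Two assumptions are needed. The means are read as control, MOD-INT, HIGH-INT, which is the natural reading and the order of the arms in the Figure 3 study flow. Pairwise tests are taken as two-sided, with one-sided results also shown.

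**Step 1: reproduce the stated power (omnibus F).**
- Grand mean = (-.112 + .124 + .200)/3 = .0707.
- Sum of squared deviations = .03337 + .00284 + .01673 = .05294.
- Noncentrality = n × .05294/.250² (12.7 at n = 15, 16.9 at n = 20), with 2 and 3(n - 1) df.
- Power = .878 at n = 15 and .957 at n = 20.

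The stated .96 reproduces. The stated .85 at n = 15 does not; n = 14 gives .851. No variant tried gave both stated figures. For example, two-way error df give .876 and .957, and a least-favourable set of means with the same range gives .848 and .941.

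**Step 2: what drives that power.** The HIGH-INT versus MOD-INT share of the between-group sum of squares is (.076²/2)/.05294 = 5.5%. The remaining 94.5% is exercise versus control. With intensity given no effect at all, omnibus power at 15 and 20 per group is:
- .734 and .861 if both exercise means are .124;
- .858 and .947 if both are .162, the average of .124 and .200.

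**Step 3: power for each pairwise contrast.** Noncentral t, pooled error with 3n - 3 df, SE = .250 × √(2/n). For HIGH-INT versus MOD-INT at n = 20, SE = .0791 and the noncentrality is .076/.0791 = 0.96.

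| Contrast | Difference (L/min) | n = 15 | n = 17 | n = 18 | n = 20 |
|---|---|---|---|---|---|
| HIGH-INT vs control | .312 | .916 | .946 | .957 | .973 |
| MOD-INT vs control | .236 | .714 | .769 | .793 | .835 |
| HIGH-INT vs MOD-INT | .076 | .129 | .140 | .146 | .157 |

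For HIGH-INT versus MOD-INT, a two-sample t-test gives .127 to .155, a normal approximation .130 to .159, and a one-sided contrast .204 to .244. A Bonferroni correction for three comparisons lowers the two-sided contrast to .057 to .073.

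**Step 4: what the design can show about intensity.**
- Sample size for 80% power at .076: 171 per group (two-sample t), or 170 by normal approximation.
- Difference detectable with 80% power: .262 L/min at n = 15 and .225 at n = 20, which is 3.4 and 3.0 times .076.
- Expected 95% CI half-width, t × SE: .184 at n = 15 and .158 at n = 20, more than twice .076.

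**The case against.** Four points can fairly be made for the plan.

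*The test and the arm labels are inferred.* This is true. Section 7 names neither, and the omnibus reading rests on the three-mean input, the ANOVA plan and the match at 20 per group. The sponsor should confirm it. The conclusion about Aim 1 does not depend on it: with the means read as control, moderate and high, no test of HIGH-INT against MOD-INT comes near .85.

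*Aim 1 is directional, so one-sided power may apply.* That raises the figure to .20 to .24, still far below what is stated.

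*This is a pilot.* The Specific Aims, Section 2 (Innovation) and Section 10 (Conclusion) say the results will help to power a larger R01 study. That supports an emphasis on estimation, and low power for Aim 1 is not in itself a fault in such a study. It does not make .85 to .96 the power for Aim 1. Section 9 (Potential Pitfalls) also plans for CRF results that do not support the hypothesis, and non-significance is the expected outcome here even if the hypothesis is true.

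*Contrasts and confidence intervals are already planned.* They are, and the intervals would show the imprecision afterwards. But none is named as primary, and the expected precision is not given.

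It is also fair to say that the gap between .85 and .878 is minor and errs on the cautious side. The finding does not rest on it.

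**Conclusion.** The concern holds. Under the plan's own means, SD and significance level, power for Aim 1 is about 13 to 16% two-sided at 15 to 20 per group, and about 14 to 15% after the expected attrition. The stated figures are more than six times as large (.85/.129 = 6.6; .96/.157 = 6.1) and describe a different question. If the true difference is .076 L/min, the trial will miss it about 84 to 87% of the time.

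This rests on reading the means as control, MOD-INT, HIGH-INT and on two-sided testing. One-sided testing does not change the conclusion. The .076 and the SD are the plan's own planning values; a larger true difference or a smaller SD would raise the power. At 20 per group, 80% power for .076 would need an SD of about .076 × .250/.225 = .084 L/min, a third of the one assumed.

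**What to change.** Rewrite the power paragraph in Section 7:

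1. Label the means by arm, state the sidedness, and name the test. Subject to the sponsor's confirmation, give .88 (15 per group) and .96 (20 per group) as power for the omnibus three-group F-test.
2. State that power for the Aim 1 contrast, HIGH-INT versus MOD-INT, is about 13 to 16% at 15 to 20 per group for the assumed .076 L/min.
3. Name that contrast as primary and report it as an estimate with its 95% confidence interval, expected half-width .16 to .18 L/min, for use in planning the R01.
4. State that neither a significant omnibus F nor a non-significant HIGH-INT versus MOD-INT contrast will be read as evidence for or against an effect of intensity.

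The cost is wording in one section. Sample size, visits and procedures stay as they are. The price is a much less favourable power figure for the main aim.
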